11.5 Annual safety reporting

The PI is also responsible for providing an annual progress report to the REC using an NRES "Annual Progress Report form for all other research". This form is available at:

<http://www.nres.npsa.nhs.uk/applications/after-ethical-review/annual-progress-reports/>

A section on the safety of participants is included in this report.

12 Statistical considerations

12.1 Randomisation

See section 9.

12.2 Sample size

Sixty young people aged 14-24 screening for early BPD, will be randomised in a 1:1 ratio to receive either a) the brief intervention plus service-as-usual or b) service-as-usual alone. Follow up will be 12 weeks and 24 weeks post-intervention. This sample size is adequate to estimate clinical parameters for recruitment and retention. Standard deviations of the putative outcome measures will facilitate power calculations for a future d-RCT.

13 Analysis

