ASSERT	Autism Symptoms SElf-reporT for adolescents and adults
BIS	Brief Impulsiveness Scale
BRIDGE	Brief Intensive Assessment and Integrated Formulation
BPD	Borderline Personality Disorder
BSL-23	Borderline Symptoms List -23
CAMHS	Children and Adolescent Mental Health Services
CAT	Cognitive Analytic Therapy
CI	Chief Investigator
CI	Confidence Intervals
CNORIS	Clinical Negligence and Other Risks Indemnity Scheme
CRN	Clinical Research Nurse
d-RCT	Definitive Randomised Controlled Trial
DSM-V	Diagnostic Statistic Manual-V
f-RCT	Feasibility Randomised Controlled Trial
GCP	Good Clinical Practice
GG&C	Greater Glasgow & Clyde
GP	General Practitioner
ICECAP-A	ICEpop CAPability measure for Adults
ISMS	Intensive Support and Monitoring Service
N	Number of Participants

NHS GG&C	National Health Service Greater Glasgow & Clyde
NHS R&D	National Health Service Research and Development
NRES	National Research Ethics Service
PHQ-9	Patient Health Questionnaire-9
PI	Principle Investigator
PIS	Patient Information Sheet
PPle groups	Patient and Public Involvement and engagement
RCT	Randomised Controlled Trial
SAE	Serious Adverse Event
SAP	Statistical Analysis Plan
SAU	Service as Usual
SDS	Sheehan's Disability Scale
SSC	Study Steering Group
YPAG	Young Person's Advisory Group

1 Synopsis

Short title	The BRIDGE project: A feasibility randomised controlled trial of brief, intensive assessment and integrated formulation for young people (age 14-24) early in the course of borderline personality disorder
Study Centre	University of Glasgow & NHS GG&C
Duration of Study	36 months
Objectives	To assess the feasibility of conducting a randomised controlled trial (f-RCT) of a BRIDGE, a brief intervention programme for young people (age 14-24) with early BPD (sub-threshold or threshold) in the general population of Glasgow, Scotland.
Primary Objectives	Are young people with early BPD willing to be randomised to BRIDGE (AND service as usual) or service as usual (ALONE) and can sufficient numbers of young people be recruited and retained such that a full-scale RCT is likely to be feasible?
Primary outcome	The two primary outcomes of this f-RCT are i. recruitment rates and ii. retention rates. The study will investigate the acceptability and appropriateness of our putative outcome measures for a future definitive randomised controlled trial (d-RCT).

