3.2 Rationale

The worldwide social and health inequality gap is widening due to Covid-19 and will have serious implications for this most vulnerable group. Scalable approaches to mitigate the long-term psychiatric and social effects of BPD, for the benefit of the whole population, is a public health priority now, more than ever (11). This study builds on pilot work demonstrating that multi-modal recruitment methods, with excellent service user consultation, can achieve high recruitment rates of young people considered hard-to-reach. Having previously demonstrated effective recruitment from within this population, the present study seeks to assess the feasibility of conducting a randomised controlled trial of a brief intervention programme for young people aged 14-24 with sub- or full- threshold BPD, (i.e. 'early BPD') in the general population of Glasgow, Scotland.

Primarily, we want to find out if recruitment and retention rates to a brief intervention for BPD symptoms in young people, are adequate to suggest a future full-scale RCT would be possible. Furthermore, we seek to investigate the acceptability and appropriateness of accepted outcome measures for a future definitive randomised controlled trial (d-RCT) which include, at the two follow-ups: [i.] psychosocial functioning [ii.] Quality of life [iii.] emotional regulation [iv.] severity of depression [v.] impulsivity [vi.] severity of self-reported BPD symptoms. We will also attempt to capture care pathways for all participants, for the purposes of future modelling of health economics impacts, in relation to putative quality of life and functional outcomes measures. The findings will inform whether to progress to a definitive RCT and, if so, the design of a definitive trial of the BRIDGE intervention for the researchers to take forward to a large funder. It will also provide a more robust level of medium term evaluation of a BPD intervention for this population

than has previously been available, aiding practitioners and service managers in their decisions relating to BPD service provision.

Timeliness:

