5.1.2 Intervention

Brief, intensive assessment and integrated formulation (BRIDGE) intervention development has been guided by a) the emerging evidence base for Cognitive Analytic Therapy (CAT) with young people (age 15-25) with BPD in an early intervention service and b) in collaboration with an established Glasgow intervention programme, called Intensive Support and Monitoring Service (ISMS), used in the Glasgow youth justice system. ISMS has the explicit focus of reaching a shared formulation with the young person and the multi-agency system that supports them.

BRIDGE is delivered over 3-6 months and has a three-fold focus:

Firstly, an intensive (post-randomisation) assessment, taking up to two sessions, including BPD symptoms, copresenting difficulties, neurodevelopmental profile, life events history and psychosocial functional impact.

Secondly, up to 16 sessions of Cognitive Analytic Therapy (CAT).

Thirdly, development of a shared formulation with a multi-agency group; further development of the shared formulation with the young person, using CAT principles (Reformulation, Recognition and Revision) and, where clinically applicable, their family and service-providers.

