5.1.3 Comparison

For participants randomised to Service-As-Usual (SAU), a routine letter of their participation will be shared with their service provider(s), including the GP. SAU, likely to range from social services, mental-health services, forensic services to no intervention will be mapped and described for each participant. Treatment fidelity to SAU will therefore not be assessed, but the nature and intensity of SAU in different contexts will be described in detail through the qualitative process evaluation.

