5.2 Procedure

Our three-month pre-trial set-up phase will establish a detailed system for managing referrals and randomisation and network between the various services from whom we would receive referrals (see section 5.1.1), including any self-referrals/completed online questionnaires. All potential participants will receive a 'Participant Information Leaflet' and a 'Trial Consent Form' prior to Screening 1.

On completion of the Participant Information sheet (online or paper format) and consent form from young people (age 14-24), and from parents and assent from children (age 14-16 who are judged by a healthcare professional as incapable of providing consent), the trial research team (trial manager and research associate) will ensure eligible adolescents and young people are invited to screening 2 with a clinician, prior to study randomisation. Capacity to consent will be confirmed and documented by a healthcare professional at screening 2, prior to randomisation.

Randomisation will be controlled by the Trial Team at the University of Glasgow, who will randomise patients (1:1) to BRIDGE (+SAU) or SAU. The trial manager will generate a randomisation list to ensure data collector blindness. The randomisation list containing the unique study ID and participant name will be stored in a password protected file within the Trial Team's private Microsoft Teams channel (following GDPR guidelines at the university of Glasgow secure server), and access will be restricted only to those members of the research team who will remain unblinded throughout the study. A log of access will be maintained.

All participants consenting to participate will be invited to complete assessments, post randomisation, at baseline, 12 and 24 weeks follow up. A minimum data set of care pathways will be described at baseline and follow-up for all participants, for the purposes of future modelling of health economics impacts, in relation to putative quality of life and functional outcomes measures. Case-study methodology will be used to understand individual contexts, involving qualitative interviews with fourteen young people (seven from BRIDGE intervention and seven from SAU's) and, where possible, their parents and relevant service providers. Topics will include acceptability of the three elements of BRIDGE, perceived mechanisms of change and exploration of requirements for data collection for a future d-RCT, including for future health economic evaluation.

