5.3 Measures

The putative outcome measures for baseline and follow-up assessments have been selected after consulting the Delphi report from International Committee for Harmonization of Outcome Measures for Personality Disorder (http://www.netscc.ac.uk/hsdr/files/project/SDO_FR_08-1404-083_V0_1.pdf). The f-RCT will investigate the acceptability and appropriateness of these measures for a future d-RCT which include, at screening/pre-randomisation: SCID-II PQ-BPD;

SCID-II DSM-V (BPD module); KIDSCREEN10; Pathways to Care and Demographics. Post randomisation: Mini International Neuropsychiatric Interview (MINI) 7.0.2 (18yrs+) and the Mini International Neuropsychiatric Interview (MINI-KID) 7.0.2 (under 18yrs); Adverse Childhood Experiences Scale; Autism Symptoms adolescents (ASSERT); Adult ADHD Self-Report Scale (ASRS). Baseline and follow-up: Borderline symptoms list (BSL-23); Sheehan's Disability Scale (SDS); Difficulties in Emotional Regulation Scale-SF; Patient Health Questionnaire-9; Quality of Life Questionnaire (EQ-5D); ICECAP-A; Suicidal Ideation Scale; Vocational and Educational functioning.

All the measures will be incorporated into a user-friendly questionnaire “book” and participants will have the option of completing on paper, in a telephone interview, or a mixture – a technique that has worked well in previous studies. These measures will be conducted, blind to group status, before and 12 and 24 weeks post randomization.

Analyses carried out in the f-RCT will remain blinded. Recruitment, retention rates and the BRIDGE sessions attended will be calculated with 95% confidence intervals (CI). A simple descriptive analysis of recruitment / retention relative to eligible / approached population will be conducted. While underpowered, between-group change in each measure after adjustment for baseline will be estimated using analysis of covariance (ANCOVA).

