7.2 Data Collection forms

A user-friendly booklet will be developed by the trial team incorporating relevant demographic and health economic information, as well as the following psychometrics:

Table 1. Baseline and follow-up assessments for the feasibility trial (The BRIDGE project)

Measure*	Baseline	12 wks	24 wks	What measuring?
Questionnaires				
SCID-II PQ-BPD	✓	✓	✓	BPD symptoms (self-reported)
SCID-II DSM-V (BPD module)	✓	✓	✓	BPD criteria (>3 or above out of 9 domains)
KIDSCREEN10	✓	✓	✓	Overall Functioning
Care pathways record and minimum data set	✓			Demographics, pathways to care
Questionnaires				Intensive assessment (BRIDGE)
K-SADS/PL	✓			Assessment of lifetime and present psychopathology
Adverse Childhood Experiences Scale	✓			Adverse childhood experiences
Autism Symptoms adolescents (ASSERT)	✓			Autism assessment
Adult ADHD Self-Report Scale (ASRS)	✓			ADHD symptom checklist
Putative outcome measures of change				Possible mechanisms of change
Borderline symptoms list (BSL-23)	✓	✓	✓	BPD symptom severity
Sheehan's Disability Scale (SDS)	✓	✓	✓	Functioning: work/school, social and family life
Difficulties in Emotional Regulation Scale-SF	✓	✓	✓	Domains of emotional regulation
Patient Health Questionnaire-9	✓	✓	✓	Severity of depression
Quality of life Questionnaire (EQ-5D)	✓	✓	✓	General health related quality of life

ICECAP-A	✓	✓	✓	Wellbeing assessment (Economic Evaluation)
Suicidal Ideation Scale	✓	✓	✓	Suicidal thinking and behaviours (ideation, self-harm, attempts)
Vocational and Educational functioning	✓	✓	✓	School and work (Paid and Unpaid) engagement

* The outcome measures for baseline and follow-up assessments have been selected after consulting the Delphi report from International Committee for Harmonization of Outcome Measures for Personality Disorder (http://www.netscc.ac.uk/hsdr/files/project/SDO_FR_08-1404-083_V01.pdf)

8 Randomisation

Randomisation will be controlled by the Trial Team at the University of Glasgow, who will randomise participants (1:1) to BRIDGE (+SAU) or SAU (see section 10). The trial manager will generate a randomisation list to ensure data collector blindness. The randomisation list will be stored in a password protected file within the Trial Team's private Microsoft Teams channel, and access will be restricted only to those members of the research team who will remain unblinded throughout the study. A log of access will be maintained.

9 Withdrawal & loss to follow-up

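### Sections 6.2 and 12.2 count the 12- and 24-week follow-ups from the end of the intervention, section 5.3 counts them from randomisation, and no visible section names the time point for retention, a primary outcome

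*Combined protocol and SAP*

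**What the plan says.** Four places set the timing of follow-up.

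- Sections 6.2 and 12.2 use the same sentence: "Follow up will be 12 weeks and 24 weeks post-intervention".
- Section 5.3: "These measures will be conducted, blind to group status, before and 12 and 24 weeks post randomization".
- Section 5.2: "All participants consenting to participate will be invited to complete assessments, post randomisation, at baseline, 12 and 24 weeks follow up". This leans towards randomisation but does not say outright where the 12 and 24 weeks start.
- Table 1 in section 7.2 has columns for baseline, 12 weeks and 24 weeks, with no anchor.

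On the two arms, section 5.1.2 says "BRIDGE is delivered over 3-6 months and has a three-fold focus", and section 5.1.3 says of the comparator: "SAU, likely to range from social services, mental-health services, forensic services to no intervention will be mapped and described for each participant".

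On the outcome, the synopsis says "The two primary outcomes of this f-RCT are i. recruitment rates and ii. retention rates". Section 3.2 refers to measures "for a future definitive randomised controlled trial (d-RCT) which include, at the two follow-ups", so there are two candidate visits. Section 13.2 gives retention with a 95% confidence interval and an ANCOVA of each measure adjusted for baseline, but names no visit for either. Sections 4.2 and 9 mention retention without a time point as well.

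**The concern.** The two anchors give different calendars. They coincide only if the intervention takes no time, and it takes 3-6 months.

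The post-intervention rule also cannot be applied to everyone. A participant on service as usual alone, who may have no service at all, has no end of intervention. In the BRIDGE arm the end varies between participants. It is unclear for those withdrawn from the intervention (section 9) or who attend few of the sessions, and these are the people who matter most for retention.

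Retention depends on how long after randomisation it is measured, so an unclear clock makes a primary outcome unclear. If the two arms were seen on different clocks:

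- by-arm retention and the ANCOVA would compare unlike times;
- the standard deviations meant for the definitive trial's power calculation (sections 6.3 and 12.2) would mix time points;
- the timing of a visit could reveal allocation to assessors who are meant to be blind.

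**Working it through.** The plan has no retention figure to reproduce. Section 6.3 declines a formal sample size calculation, and N=60 is not in dispute here.

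**Inputs from the documents:** delivery over 3-6 months (5.1.2); visits at 12 and 24 weeks (5.3, 6.2, 12.2); 60 participants randomised 1:1, so about 30 per arm (12.2).

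**Assumptions:** therapy starts at randomisation; dropout is constant over time; 24-week retention is 90%, 80% or 70%.

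**Step 1, calendar.** Weeks = months × 365.25 / 12 / 7, so 3 months = 13.0 weeks and 6 months = 26.1 weeks.

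| Visit | Counted from randomisation (5.3) | Counted from end of BRIDGE (6.2, 12.2) | Service as usual alone, post-intervention rule |
|---|---|---|---|
| 12 weeks | 12 | 13.0 + 12 = 25.0 to 26.1 + 12 = 38.1 | undefined |
| 24 weeks | 24 | 13.0 + 24 = 37.0 to 26.1 + 24 = 50.1 | undefined |

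The readings differ by 13.0 to 26.1 weeks at each visit. With an assumed 4-week wait before therapy, the last visit moves to weeks 41.0-54.1.

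**Step 2, BRIDGE-arm retention.** With constant dropout and 24-week retention r, retention at week t is r^(t/24). The exponents are 37.04/24 = 1.543 and 50.09/24 = 2.087.

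| r at week 24 | Week 37.0 | Week 50.1 | Drop (points) | Exact 95% CI for r with n = 30 |
|---|---|---|---|---|
| 90% | 85.0% | 80.3% | 5.0 to 9.7 | 27/30: 73.5-97.9% |
| 80% | 70.9% | 62.8% | 9.1 to 17.2 | 24/30: 61.4-92.3% |
| 70% | 57.7% | 47.5% | 12.3 to 22.5 | 21/30: 50.6-85.3% |

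In people, this is 0.050 × 30 = 1.5 to 0.225 × 30 = 6.7 of about 30. The intervals are Clopper-Pearson. Five of the six shifted values lie inside them; only 47.5% lies outside. In a trial this small, then, the shift would be hard to tell from chance in the data. That does not make it harmless: it is a systematic difference added to sampling error.

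**Step 3, pooled retention.** If service as usual alone were seen 24 weeks after randomisation with the same r (assumption), only half the sample shifts. The overall rate then falls by half of each drop: 2.5 to 4.9, 4.6 to 8.6 and 6.2 to 11.2 points.

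**The case against.** The strongest reply is that this is a wording slip. One sentence appears twice, in the population and sample-size sections, while the section that specifies how measures are taken gives a usable anchor. Section 9 expects little loss because contact with participants is not long, which fits 24 weeks better than 37-50. Since the post-intervention rule cannot be run for service as usual alone, a site would probably not follow it, and no section describes seeing the arms on different clocks. This may well be so, but staff still face two written rules.

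A second reply is that section 13.1 promises a separate SAP, and that the flow diagram (2.1) and timelines (19) are not readable here; any of these may name the retention visit. That is a fair limit on the statement that no time point is given. It does not remove the contradiction between 5.3 and 6.2/12.2.

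A third reply concerns size. Section 13.2 does not say that retention is reported by arm, so the pooled shift is closer to the plan than the BRIDGE-arm shift. All the retention percentages rest on assumptions. This stands: only the calendar difference comes from the documents' own figures, and even that needs an assumed start of therapy to give weeks from randomisation.

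Finally, the sponsor may have wanted assessments after treatment, since section 3.2 speaks of medium-term evaluation. With 6-month delivery, weeks 12 and 24 after randomisation both fall during therapy, so those participants would have no post-treatment assessment. This is a real cost of anchoring the present visits to randomisation, and the sponsor has to weigh it.

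**Conclusion.** The concern holds. The protocol gives two incompatible rules for the same visits, and one of them yields no date in the control arm. This is an error in the text and not merely missing detail. It should be fixed because it sits under a primary outcome and the between-group estimates. The gap of about 13 to 26 weeks follows from the stated delivery period. The retention shifts show what that gap could do under assumed dropout; they do not predict what this trial will see. With no visible progression threshold, the ambiguity cannot be shown to change a stated decision. Confidence in the contradiction is high. The lack of a retention time point is established only for the sections that can be read.

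**What to change.** Use one anchor that is defined in both arms. Of the two in the text only randomisation qualifies.

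1. In 6.2 and 12.2, replace the post-intervention anchor with randomisation.
2. In Table 1, label the 12- and 24-week columns as weeks after randomisation.
3. In 13.2 or the SAP, define retention as the number assessed at 24 weeks after randomisation divided by all randomised, by arm and overall, with 95% confidence intervals. Also report 12-week retention, and name the ANCOVA time points. Reconcile this denominator with the description in 13.2 of retention relative to those eligible or approached.
4. If later visits were intended, set them at fixed weeks after randomisation in both arms.

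While editing, reconcile 5.2, which lists baseline among the post-randomisation assessments, with the synopsis, which has baseline completed before randomisation.

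Items 1-3 need wording only, with no extra visits or participants. Appendix 1 shows that the trial is under way, so the change needs steering committee agreement (17.2) and, if substantial, ethics review (16.1). If visits have in practice been timed from the end of therapy, the edit alters a running schedule; anyone already assessed on that basis should be reported with actual assessment dates. Some BRIDGE participants will still be in therapy at a visit: week 12 precedes the end of a 3-month course (week 13), and week 24 the end of a 6-month one (week 26). The report should say so.

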13.1 Statistical Analysis Plan

The study will have a comprehensive Statistical Analysis Plan (SAP), which will govern all statistical aspects of the study, and will be authored by the Trial Team in collaboration with a supporting Statistician before any unblinded data is seen.

The Robertson Centre for Biostatistics, part of the Glasgow Clinical Trials Unit, a fully registered UK CRN Clinical Trials Unit, will support and advise on data analysis.

13.2 Main analysis

All statistical analyses will be pre-specified in a detailed Statistical Analysis Plan, to be finalised prior to unblinding of intervention groups, and agreed by the Trial Steering Group.

Analyses carried out in the f-RCT will remain blinded. Recruitment, retention rates and the BRIDGE sessions attended will be calculated with 95% confidence intervals (CI). A simple descriptive analysis of recruitment / retention relative to eligible / approached population will be conducted. While underpowered, between-group change in each measure after adjustment for baseline will be estimated using analysis of covariance (ANCOVA).

Economic analysis

For the economic analysis, data will be collected on cost of delivering the intervention in addition to participant use of health, personal social services and broader educational and societal resources.

Qualitative analysis

Interviews will be transcribed verbatim and subject to a thematic analysis, where re-occurring topics/issues are identified across the dataset using rigorous qualitative analytical techniques.

14 Data management

A Data Management Plan will be developed for the study in line with approved templates, reviewed regularly and all members of the project team will adhere to the plan.

The study team works in line with General Data Protection Regulations (2018). All participants will be identified by a study specific number. No names or other personal identifiers will be used in data collection forms. Since name and address information are needed for participant's follow up, the research team will use a master list matching study identifiers to this personal information. However, this list will be password protected, used only by the immediate study team and be kept in a study file accessible to only study team on a secure server within Research Institution. This information as indicated above will be kept separate from the research data, which constitute the research outputs of this study. Copies of consent forms will be kept in a locked filing cabinet in an office with a limited access to research team only. All assessment and questionnaire forms will only bare study specific ID number. Audio recordings will not directly address participants by their names but rather study specific number. Any personal details and any other identifying characteristics will be removed before being stored in password protected file accessible by the research team only on secured University Servers or the secure trial MS Teams page.

15 Trial closure

The trial will end when the SSC agrees that one or more of the following situations applies:

- 1) The planned sample size has been achieved, and follow-up is complete;
- 2) There is insufficient funding to support further recruitment, and no reasonable prospect of additional support being obtained;
- 3) New information makes it inappropriate to continue to randomise patients to one or other arm of the trial;
- 4) Recruitment is so poor that completion of the trial cannot reasonably be anticipated.

16 Regulatory issues

